PROs (Electronic)												
Complete prior to any clinical administered assessments												
DLQI		X					X		X	X		Only for participants ≥16 years of age at baseline.

	Period I	Period II									Period III	Comments
	Screening	Baseline	Treatment Period									
Visit Number	1	2	3	4	5	6	7	8	9	ED	801	
Week Relative to Study Drug Start	≤30 (days)	0	2	4	8	12	16	20	24	-	Approximately 12 weeks post last dose	
Visit Interval Tolerance (Days)		-	±3	±3	±5	±5	±5	±5	±5	-	±7	
Visit Detail						T		T				
cDLQI		X					X		X	X		Only for participants <16 years of age at baseline.
WPAI-AD		X					X		X	X		
ADCT		X		X			X		X	X		
Participant-Reported Satisfaction Question							X		X	X		
Clinical-Administered Assessments (Electronic)												
IGA	X	X	X	X	X		X		X	X		
F-IGA		X	X	X	X		X		X	X		
EASI	X	X	X	X	X		X		X	X		
BSA	X	X	X	X	X		X		X	X		
mTLSS		X		X			X		X	X		
SCORAD		X					X		X	X		
Clinical-Administered Assessments (Paper)												
Fitzpatrick Skin Type Assessment		X										

	Period I	Period II									Period III	Comments
	Screening	Baseline	Treatment Period								Post-Treatment Follow-up	
Visit Number	1	2	3	4	5	6	7	8	9	ED	801	
Week Relative to Study Drug Start	≤30 (days)	0	2	4	8	12	16	20	24	-	Approximately 12 weeks post last dose	
Visit Interval Tolerance (Days)		-	±3	±3	±5	±5	±5	±5	±5	-	±7	
Visit Detail						T		T				
Participant Education and Supplies												
Participant or caregiver instructions on diary completion	X											Education can also be performed, as needed.
Remind participant of TCS usage restrictions and expectations	X											Required 2 week wash out of TCS prior to Visit 2. See Section 6.8.1 for TCS usage during the study.
Train participant and/or caregiver on study intervention administration			X	X								Participants and/or caregivers need to be adequately trained on injection technique prior to administering injections. Training can be done at Week 2 and/or Week 4 prior to self-administration.
Dispense ancillary supplies for at home dosing				X	X		X					
Laboratory Tests and Sample Collections												
Hematology	X	X		X			X		X	X	X	
Clinical chemistry	X	X					X		X	X	X	

	Period I	Period II									Period III	Comments
	Screening	Baseline	Treatment Period								Post-Treatment Follow-up	
Visit Number	1	2	3	4	5	6	7	8	9	ED	801	
Week Relative to Study Drug Start	≤30 (days)	0	2	4	8	12	16	20	24	-	Approximately 12 weeks post last dose	
Visit Interval Tolerance (Days)		-	±3	±3	±5	±5	±5	±5	±5	-	±7	
Visit Detail						T		T				

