Serum pregnancy	X											Only for WOCBP. Pregnancy tests prior to first dose of study intervention for females ≥12 years of age if menarche reached or if there is reason to believe the participant is sexually active. Pregnancy test results from baseline must be known prior to first dose of study intervention. See Section 10.4, Appendix 4.
Urine pregnancy (local)		X		X	X		X		X	X		Collect for WOCBP only. Done locally and prior to administering study intervention. Additional pregnancy tests (beyond those required per the SoA) should be performed at any time during the trial if a menstrual period is missed, there is clinical suspicion of pregnancy. See Section 10.4, Appendix 4. If required per local regulations and/or institutional guidelines, pregnancy testing can occur at other times during the study treatment period.
HIV screening tests	X											
HCV screening tests	X											If anti-HCV is positive, it must be followed by a HCV RNA test. See Section 8.2.4.
HBV screening tests	X											Includes testing for HBsAg, HBcAb and HBsAb.

	Period I	Period II									Period III	Comments
	Screening	Baseline	Treatment Period									
Visit Number	1	2	3	4	5	6	7	8	9	ED	801	
Week Relative to Study Drug Start	≤30 (days)	0	2	4	8	12	16	20	24	-	Approximately 12 weeks post last dose	
Visit Interval Tolerance (Days)		-	±3	±3	±5	±5	±5	±5	±5	-	±7	
Visit Detail						T		T				
HBV DNA	X						X			X	X	If HBsAg is negative and HBcAb is positive at screening, further testing for HBV DNA is required. See Section 8.2.3.
IgE		X		X			X		X	X		Collect prior to dosing.
Exploratory Biomarkers		X		X			X		X	X		Collect prior to dosing.
PK samples		X		X					X	X		Samples to be collected predose. If an immediate or nonimmediate systemic drug hypersensitivity reaction occurs in any participant, then also collect an additional unscheduled sample as detailed in Section 8.4.
Immunogenicity (ADA) samples		X		X					X	X		Samples to be collected predose. If an immediate or nonimmediate systemic drug hypersensitivity reaction occurs in any participant then also collect an additional unscheduled sample as detailed in Section 10.2.1.
Stored Samples												
Genetics sample		X										Sample can be obtained at or after the specified visit.
Exploratory biomarker samples		X		X			X		X	X		Collect predose.

	Period I	Period II									Period III	Comments
	Screening	Baseline	Treatment Period								Post-Treatment Follow-up	
Visit Number	1	2	3	4	5	6	7	8	9	ED	801	

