Week Relative to Study Drug Start	≤30 (days)	0	2	4	8	12	16	20	24	-	Approximately 12 weeks post last dose	
Visit Interval Tolerance (Days)		-	±3	±3	±5	±5	±5	±5	±5	-	±7	
Visit Detail						T		T				
Registration and Dosing												
Register visit with IWRS	X	X	X	X	X	X	X	X	X	X	X	
Dispense study intervention via IWRS		X	X	X	X		X					
Administer study intervention in clinic		X	X	X	X		X					Week 0 (Visit 2) and Week 2, dose to be administered in the clinic by site. Weeks 4, 8, and 16 dosing to be performed in clinic administered by site or participant or caregiver.
Dispense study intervention to participant for at home dosing				X	X		X					Injections will be administered by participant or caregiver at home on Weeks 6, 10, 12, and 14. Responders at Week 16 who will receive Q4W dose will administer study intervention at Week 20. Inadequate responders at Week 16 who will receive Q2W dosing will administer study intervention at Weeks 18, 20, and 22.
Observe participant or caregiver administer study intervention				X								

	Period I	Period II									Period III	Comments
	Screening	Baseline	Treatment Period									
Visit Number	1	2	3	4	5	6	7	8	9	ED	801	
Week Relative to Study Drug Start	≤30 (days)	0	2	4	8	12	16	20	24	-	Approximately 12 weeks post last dose	
Visit Interval Tolerance (Days)		-	±3	±3	±5	±5	±5	±5	±5	-	±7	
Visit Detail						T		T				
Participant returns study intervention					X		X		X	X		If study intervention was administered at home by participant or caregiver, the injection supplies should be saved and returned at the next on-site visit.
Assess study intervention compliance					X		X		X			

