7.1. Discontinuation of Study Intervention

When necessary, a participant may be permanently discontinued from study intervention. If so, the participant will remain in the study to complete procedures for an early discontinuation visit and post-treatment follow-up, if applicable, as shown in the SoA.

A participant should be permanently discontinued from study intervention if

- the participant becomes pregnant during the study
- in the opinion of the investigator, the participant should permanently discontinue the study intervention for safety reasons
- the participant develops a malignancy, except for successfully treated basal or squamous cell skin carcinoma
- the participant tests positive for HBV DNA (see Section 8.2.3)
- the participant tests positive for HCV RNA (Section 8.2.4)
- if the participant experiences a hepatic event or liver test abnormality as specified in the liver chemistry stopping criteria (see Section 7.1.1)
- the participant develops HIV infection
- the participant requires rescue medication treatment for symptoms of AD in the treatment period
- the participant develops any infection that is opportunistic, such as active tuberculosis and other infections whose nature or course may suggest an immuno-compromised status, and
- the participant has an AE or an SAE or a clinically significant change in a laboratory value that, in the opinion of the investigator, merits discontinuation of study intervention and appropriate measures being taken.

Hepatitis

- prior to discontinuation of any immunomodulatory and/or immunosuppressive therapy due to hepatitis, including study intervention, the participant is to be referred to, evaluated, and managed by a specialist physician with expertise in evaluation and management of viral hepatitis.
- the timing of discontinuation from study intervention relative to the initiation of any antiviral treatment for hepatitis is to be based on the recommendation of the consulting specialist physician, in conjunction with the investigator, and aligned with medical guidelines and standard of care.

Hypersensitivity

- if the investigator determines that a systemic hypersensitivity reaction has occurred related to study intervention administration, the participant may be permanently discontinued from the study intervention, and the sponsor's designated medical monitor

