7.1.2. Temporary Discontinuation of Study Intervention

Temporary withholding of study intervention is required if the participant meets any of the following infection-related criteria during the study:

- Serious or opportunistic infections, as defined in Section 5.2. Study intervention is to be withheld until resolution of all acute clinical signs and symptoms, and completion of all appropriate anti-infective treatment.
- HBV DNA results that are reported as positive, or as detecting HBV DNA, but HBV DNA is below the level of quantification. In this situation, the sponsor's designated medical monitor should be contacted regarding the participant's status. HBV DNA testing is to be repeated as soon as is feasible. If HBV DNA is confirmed as positive, the participant must be permanently discontinued from study intervention as described in Section 7.1.
- If a participant <18 years of age loses a clinically significant amount of weight (below 40 kg), the investigator should assess rationale for weight loss and use clinical judgment to determine if the participant should temporarily discontinue the treatment.

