8.2.3. Hepatitis B Testing and Monitoring

As specified in the SoA (Section 1.3), initial testing for HBV infection includes HBsAg and hepatitis B core antibody (HBcAb).

- If HBsAg is positive, the participant is excluded.
- If HBsAg is negative and HBcAb is negative, the participant is not excluded.
- If HBsAg is negative and HBcAb is positive, further testing for HBV DNA is required.
 - If the screening HBV DNA is positive, the participant is excluded.
 - If the screening HBV DNA is negative, the participant is not excluded. Repeat testing for HBV DNA is required at least every 3 months during the study as described in the SoA.

Management of enrolled participants with detectable HBV DNA during the study

If HBV DNA is detected, study intervention will be temporarily withheld or permanently discontinued, as described in Sections 7.1.2 and 7, and the participant should be referred for appropriate follow-up medical care.

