10.2. Appendix 2: Clinical Laboratory Tests

- The tests detailed in the table below will be performed by the central laboratory.
- In circumstances where the sponsor approves local laboratory testing in lieu of central laboratory testing (in the table below), the local laboratory must be qualified in accordance with applicable local regulations.
- Protocol-specific requirements for inclusion or exclusion of participants are detailed in Section 5 of the protocol.
- Additional tests may be performed at any time during the study as determined necessary by the investigator or required by local regulations.
- Investigators must document their review of the laboratory safety results.

Clinical Laboratory Tests	Comments
Hematology	Assayed by Lilly-designated laboratory
Hemoglobin	
Hematocrit	
Erythrocyte count (RBCs)	
Mean cell volume	
Mean cell hemoglobin	
Mean cell hemoglobin concentration	
Absolute neutrophil count (calculation) (definition – include segs and bands or segs, bands and other immature cells)	
Leukocytes (WBCs)	
Differential	
Percent and absolutes count of:	
Neutrophils, segmented	
Neutrophils, bands	
Lymphocytes	
Monocytes	
Eosinophils	
Basophils	
Platelets	
Cell morphology (RBCs and WBCs)	
Clinical Chemistry	Assayed by Lilly-designated laboratory
Sodium	
Potassium	
Chloride	
Bicarbonate	
Total bilirubin	
Direct bilirubin	
ALP	

Clinical Laboratory Tests	Comments
ALT	
AST	
GGT	
BUN	
Creatinine	
CK	
Uric acid	
Total protein	
Albumin	
Calcium	
Phosphorus	
LDH	
Hormones (female)	
Serum pregnancy	Assayed by Lilly-designated laboratory
Urine pregnancy	Assayed and Evaluated locally
HIV and Hepatitis Serology	Assayed by Lilly-designated laboratory
HIV testing	
HCV testing:	
HCV antibody	
HCV RNA	
HBV testing:	
HBV DNA	Performed only for participants who test positive for HBcAb
HBcAb	
HBsAg	
HBsAb	
Exploratory Biomarkers	Assayed by Lilly-designated laboratory Results will not be provided to the investigative sites
CCI	
Immunoglobulins	Assayed by Lilly-designated laboratory Results will not be provided to the investigative sites
IgE (Serum)	
Genetics Sample	Assayed by Lilly-designated laboratory Results will not be provided to the investigative sites
Exploratory Biomarker storage samples	Assayed by Lilly-designated laboratory Results will not be provided to the investigative sites
Serum	

Clinical Laboratory Tests	Comments
Immunogenicity (ADA) samples	Assayed by Lilly-designated laboratory Results will not be provided to the investigative sites

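### For HBcAb-positive participants the Schedule of Activities spaces HBV DNA tests 16 to 20 weeks apart, while Section 8.2.3 sets a 3-month limit, and the first gap spans dosing

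*Protocol*

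**What the plan says.** Protocol Section 8.2.3 does not exclude a participant who is surface-antigen negative and core-antibody positive, provided that HBV DNA is negative at screening. For that participant it adds: "Repeat testing for HBV DNA is required at least every 3 months during the study as described in the SoA".

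The HBV DNA row of the SoA (Protocol Section 1.3) has marks at Visit 1 (screening), Visit 7 (Week 16), ED and Visit 801, and nowhere else. Its comment gives no further times and points back to the text: "If HBsAg is negative and HBcAb is positive at screening, further testing for HBV DNA is required. See Section 8.2.3".

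A positive result has consequences for dosing. Section 7.1 lists it as a reason to stop study drug permanently. Section 7.1.2 requires the drug to be withheld while a result below the level of quantification is repeated, and then: "If HBV DNA is confirmed as positive, the participant must be permanently discontinued from study intervention as described in Section 7.1".

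**The concern.** Section 8.2.3 sets a limit and names the SoA as the means of meeting it, but the SoA does not meet it. A site that follows the SoA to the letter will be out of compliance with Section 8.2.3 for every HBcAb-positive participant who reaches Week 16 and Visit 801.

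The stopping rules in Sections 7.1 and 7.1.2 act only on a test result. In the first gap, participants are dosed from Week 0 to Week 14 with no scheduled HBV DNA test after screening. The "Clinical chemistry" row has no mark between baseline and Week 16 either, so routine liver chemistry gives no indirect signal. There is also no clinic visit between Week 8 and Week 16 at which the omission would be noticed, because Week 12 is a telephone visit and the doses around it are given at home: "Injections will be administered by participant or caregiver at home on Weeks 6, 10, 12, and 14".

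**Working it through.** **Inputs**

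- Limit: 3 months, taken as 91 days (13 weeks). Calendar readings run from 89 to 92 days.
- Screening: 0 to 30 days before baseline (Protocol 4.1).
- Normal visit windows: ±3 days at Week 4; ±5 days at Weeks 8, 16 and 24; ±7 days at Visit 801 (SoA).
- Last dose: Week 20 for Week 16 responders (Q4W). For the others (Q2W): "Inadequate responders at Week 16 who will receive Q2W dosing will administer study intervention at Weeks 18, 20, and 22".
- Visit 801: about 12 weeks after the last dose, hence Week 32 (Q4W) or Week 34 (Q2W).

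**Check on the timeline.** 30 days + (22 + 12) weeks = 268 days = 38.3 weeks, which agrees with the planned maximum of 38 weeks in the synopsis. Week 34 is also the Visit 801 timing in SAP Section 4.1.

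**Check on the table.** Read by column in the same way, the chemistry row gives Visits 1, 2, 7, 9, ED and 801. The HBV DNA row is therefore not a misaligned extract.

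**Scheduled gaps between HBV DNA tests**

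| Interval | Nominal | With normal windows |
|---|---|---|
| Screening to Week 16 | 16×7 = 112 d, up to 112+30 = 142 d (16.0 to 20.3 wk) | 112−5 = 107 to 142+5 = 147 d |
| Week 16 to Visit 801, Q4W | (32−16)×7 = 112 d (16 wk) | 112±(5+7) = 100 to 124 d |
| Week 16 to Visit 801, Q2W | (34−16)×7 = 126 d (18 wk) | 126±12 = 114 to 138 d |

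The window column assumes that the last dose falls on its nominal day. The smallest entry, 100 days, exceeds any reading of 3 months.

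**When the first repeat falls due**

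- Screening on the baseline day: day 91 = Week 13.0. At Week 16 it is 112−91 = 21 days (3.0 weeks) overdue, and 1 dose (Week 14) has been given after the due date.
- Screening 30 days earlier: day 91−30 = 61 = Week 8.7. At Week 16 it is 112−61 = 51 days (7.3 weeks) overdue, and 3 doses (Weeks 10, 12 and 14) have been given after the due date.

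**Exposure before the Week 16 test.** Weeks 0 to 14 hold 8 dosing occasions: 2+2+6×1 = 10 injections, or 10×250 = 2,500 mg.

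**Second gap.** Week 16 + 91 days = Week 29, which is after the last main-study dose at Week 20 or 22.

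**The case against.** The best defence is that a site can satisfy both passages. The SoA comment refers the reader to Section 8.2.3, and Appendix 2 states: "Additional tests may be performed at any time during the study as determined necessary by the investigator or required by local regulations". Adverse events are reviewed at every visit, including the Week 12 call, and the investigator may stop the drug for safety at any time. This stands as mitigation: compliance is possible through an unscheduled draw. It does not remove the conflict. Appendix 2 is permissive where Section 8.2.3 is mandatory, Section 8.2.3 says that the SoA describes the testing, and nothing in the SoA prompts the draw. Reading the SoA as controlling would leave the 3-month limit with no meaning.

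Three points of scale are fair:

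- Most of the 2,500 mg would be given under a compliant schedule too. With the first repeat on its due date, 5 to 7 of the 8 dosing occasions (7 to 9 injections) come first. The excess due to the conflict is 1 to 3 injections, or 250 to 750 mg.
- Screening on the baseline day is not realistic, because the diary is dispensed at screening and should be completed on at least 4 of the 7 days before baseline. With 4 days the gap is 112+4 = 116 days and the test falls due on day 87. One dose is still given late, so the true minimum is slightly worse than the tabulated one.
- The affected subset may be small, even empty, and the primary endpoint and its analysis are untouched.

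**Conclusion.** The conflict is real. For HBcAb-positive participants who attend Week 16 and Visit 801, both scheduled gaps (112 to 142 days, then 112 or 126 days) exceed about 91 days under every normal window combination. The first gap is the important one: the repeat test is 3.0 to 7.3 weeks overdue at Week 16, and 1 to 3 doses are given in the meantime with no scheduled test that could trigger the stopping rules. In the second gap a late test delays referral for medical care rather than a main-study dosing decision.

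The conclusion rests on 3 months being about 91 days, on the normal visit windows, and on the last dose and Visit 801 falling as scheduled. It does not cover early discontinuers, whose ED test can keep them within the limit. The size of the HBcAb-positive subset is not given, so the number of people affected cannot be stated. What is at stake is participant safety and protocol compliance, not the efficacy estimate.

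**What to change.** Add HBV DNA marks to the SoA, for HBcAb-positive participants only, at Week 4 (Visit 4) and Week 24 (Visit 9). Blood is already drawn at both visits. The gaps become:

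- Screening to Week 4: 28 to 58 days (at most 61 with windows)
- Week 4 to Week 16: 84 days (at most 84+3+5 = 92)
- Week 16 to Week 24: 56 days (at most 66)
- Week 24 to Visit 801: 56 days on Q4W (at most 68) or 70 days on Q2W (at most 82)

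One window combination reaches 92 days. If every combination must stay within 91 days, use Week 8 instead of Week 4: screening to Week 8 is 56 to 86 days (at most 91), and Week 8 to Week 16 is 56 days (at most 66). Week 8 has no scheduled blood draw at present, so this option adds one venipuncture.

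The cost is two extra HBV DNA assays per HBcAb-positive participant and one edited SoA row. The edit is a protocol amendment and needs ethics approval before implementation (Protocol 10.1.1). Merely restating the 3-month rule in the SoA comment would be weaker, because the first repeat can fall due between Week 8 and Week 16, when no clinic visit is planned.

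Separately, confirm that Protocol Addendum 2, which was not available for this review, keeps testing within 3 months for Continued Access participants. SAP Section 4.1 says that they skip Visit 801.

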8.2.4. Hepatitis C Testing

As specified in the SoA (Section 1.3), initial testing for HCV infection includes testing for antibodies to HCV (anti-HCV).

- If anti-HCV is positive, a test for circulating HCV RNA is required.
- If HCV RNA test is negative, the participant is not excluded.
- If HCV RNA test is positive, the participant is excluded (see Section 5.2).

Participants who have had HCV infection and have been successfully treated, defined as a sustained virologic response (HCV RNA by polymerase chain reaction negative for at least 24 weeks following treatment completion), are not excluded on the basis of HCV as long as HCV RNA test is negative at screening.

If HCV RNA is detected during the study, the study intervention will be discontinued (Section 7), and the participant should receive appropriate follow-up medical care.

8.3. Adverse Events, Serious Adverse Events, and Product Complaints

The definitions of the following events can be found in Appendix 3:

- AEs
- SAEs, and
- PCs.

These events will be reported by the participant, or when appropriate, by a caregiver, surrogate, or the participant's legally authorized representative.

The investigator and any qualified designees are responsible for detecting, documenting, and recording events that meet these definitions and remain responsible for following up events that are serious, considered related to the study intervention or study procedures, or that caused the participant to discontinue the study intervention or study (see Section 7).

Care will be taken not to introduce bias when detecting events. Open-ended and non-leading verbal questioning of the participant is the preferred method to inquire about event occurrences.

After the initial report, the investigator is required to proactively follow each participant at subsequent visits or contacts. All SAEs and AEs of special interest, as defined in Section 8.3.3, will be followed until resolution, stabilization, the event is otherwise explained, or the participant is lost to follow-up (as defined in Section 7.3). For PCs, the investigator is responsible for ensuring that follow-up includes any supplemental investigations as indicated to elucidate nature and/or causality. Further information on follow-up procedures is provided in Section, 10.3, Appendix 3.

8.3.1. Timing and Mechanism for Collecting Events

This table describes the timing, deadlines, and mechanism for collecting events.

Event	Collection Start	Collection Stop	Timing for Reporting to Sponsor or Designee	Mechanism for Reporting	Back-up Method of Reporting
Adverse Event					
AE	Signing of the ICF	Participation in study has ended	As soon as possible upon site awareness	AE CRF	N/A
Serious Adverse Event					
SAE and SAE updates – prior to start of study intervention and deemed reasonably possibly related to study procedures	Signing of the ICF	Start of intervention	Within 24 hours of awareness	SAE paper form	SAE paper form
SAE and SAE updates – after start of study intervention	Start of intervention	Participation in study has ended	Within 24 hours of awareness	SAE paper form	SAE paper form
SAE ^a – after participant’s study participation has ended and the investigator becomes aware	After participant’s study participation has ended	N/A	Promptly	SAE paper form	N/A
Pregnancy					
Pregnancy in female participants and female partners of male participants	After the start of study intervention	At least 18 weeks after the last dose of study intervention	Within 24 hours (see Section 8.3.2)	Pregnancy paper form	Pregnancy paper form

Event	Collection Start	Collection Stop	Timing for Reporting to Sponsor or Designee	Mechanism for Reporting	Back-up Method of Reporting
Product Complaints					
PC associated with an SAE or might have led to an SAE	Start of study intervention	End of study intervention	Within 24 hours of awareness	PC form	N/A
PC not associated with an SAE	Start of study intervention	End of study intervention	Within 1 business day of awareness	PC form	N/A
Updated PC information	—	—	As soon as possible upon site awareness	Originally completed PC form with all changes signed and dated by the investigator	N/A
PC, if investigator becomes aware	Participation in study has ended	N/A	Promptly	PC form	

Abbreviations: AE = adverse event; ICF = informed consent form; N/A = not applicable; PC = product complaint
SAE = serious adverse event.

^a Serious adverse event should not be reported unless the investigator deems them to be possibly related to study treatment or study participation.

